7.10. Safety Evaluation

Safety evaluation is covered by secondary endpoints.

Listing of AEs, SAEs, ADEs and SADEs, and U(S)ADEs will be provided based on Safety Analysis Set. AEs, SAEs, ADEs and SADEs, and U(S)ADEs will be analyzed using Medical Dictionary for Regulatory Activities (MedDRA v23.1) classification per System Organ Class and Preferred Term and they will also be assessed using the potential risks identified in the Clinical Investigation Plan.

An Adverse Device Effect is an Adverse Event related to device and/or procedure.

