V2.0 – 05Nov2021	
 • Update of CIP version page 1 (V4.0) • Add Pregnancy Test (Section 5 page 7) • Demographic, risk factors and per-operative characteristics: measured on PAS, PPAS, SAS removed from Secondary Endpoints (alignment with CIP V4.0). • Update of Section 7.10 Safety evaluation is covered by secondary endpoints. 
Listing of AEs, SAEs, ADEs and SADEs, and U(S)ADEs will be provided based on Safety Analysis Set. AEs, SAEs, ADEs and SADEs, and U(S)ADEs will be analyzed using Medical Dictionary for Regulatory Activities (MedDRA v23.1) classification per System Organ Class and Preferred Term and they will also be assessed using the potential risks identified in the Clinical Investigation Plan.
 
An Adverse Device Effect is an Adverse Event related to device and/or procedure.
	[REDACTED] Sr Biostatistician, Surgical Innovations Medtronic

2. List of Abbreviations and Definitions of Terms

Term/Abbreviation	Definition
ADE	
Adverse device effect - Adverse event related to the use of an investigational medical device.
 
Note: This definition includes adverse events resulting from insufficient or inadequate instructions for use, deployment, implantation, installation, or operation or any malfunction of the investigational medical device.
 
Note: This definition includes any event resulting from use error or from intentional misuse of the investigational medical device.

Term/Abbreviation	Definition
AE	
Adverse event - Any untoward medical occurrence, unintended disease or injury, or untoward clinical signs (including abnormal laboratory findings) in subjects, users or other persons, whether or not related to the investigational medical device.
 
Note: This definition includes events related to the investigational medical device or the comparator.
 
Note: This definition includes events related to the procedures involved.
 
Note: for users or other persons, this definition is restricted to events related to investigational medical devices.

CI	Confidence Interval
CIP	Clinical Investigation Plan (can be used synonymously with Protocol)
Hernia	A clinically manifested bulge or a protrusion exacerbated by a Valsalva maneuver.
PAS	Performance Analysis Set
PMCF	Post Market Clinical Follow up
PPAS	Per Protocol Analysis Set – An analysis set a subset of the Performance analysis set, excluding subjects with major protocol deviation(s) and violation(s).
QOL	Quality of Life

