SAE	
Serious Adverse Event - Adverse event that:
 
 a) Led to a death, b) Led to a serious deterioration in the health of the subject, that either resulted in: 
 1) Resulted in a life-threatening illness or injury, or 2) Resulted in a permanent impairment of a body structure or a body function, or 3) In-patient or prolonged hospitalization, or 4) Medical or surgical intervention to prevent life threatening illness or injury or permanent impairment to a body structure or a body function, or 
Led to fetal distress, fetal death or a congenital abnormality or birth defect.
 
Note: Planned hospitalization for a pre-existing condition, or a procedure

Term/Abbreviation	Definition
	required by the CIP, without serious deterioration in health, is not considered a serious adverse event.
SADE	Serious Adverse Device Effect - Adverse device effect that has resulted in any of the consequences characteristic of a serious adverse event.
SAP	Statistical Analysis Plan
SAS	Safety Analysis Set – An analysis set including any subjects enrolled in the study.
USADE	Unanticipated Serious Adverse Device Effect - Any serious adverse device effect which by its nature, incidence, severity or outcome has not been identified in the current version of the risk analysis report. Note: Anticipated serious adverse device effect (ASADE) is an effect which by nature, incidence, severity or outcome has been identified in the risk analysis report.
VAS	Visual Analog Scale is a psychometric response scale (0-10) which can be used in questionnaires to determine how much pain a subject is feeling.

3. Introduction

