7.1.3. Analysis Sets

Statistical analysis will be performed on:

- Performance Analysis Set (PAS): includes all enrolled subjects excluding subjects who became pregnant during the follow-up, or subjects who undergo unscheduled abdominal surgery during study follow-up, which may increase the risk and cause of incisional hernia occurrence*.

*Subject follow-up data, starting from the event's occurrence, will be excluded/remove from the performance analysis.

- Per Protocol Analysis Set (PPAS): a subset of PAS excluding subjects with protocol violation and major protocol deviation(s) that may impact the primary endpoint assessment. More precisely, reason for exclusion may include but is not limited to:
 - Patient wrongly included (*i.e.* patient was enrolled but does not meet all the eligibility criteria).
 - Failure to obtain informed consent.
 - Deviation resulting from device use outside the recommended use in the IFU.
 - Patient who receives the incorrect device or device is misused
- Safety Analysis Set: includes all enrolled subjects.

Performance analyses will be run on Performance Analysis Set (PAS) and on Per Protocol Analysis Set (PPAS) as confirmatory analysis.

Safety analyses will be run on Safety Analysis set (SAS) and on Per Protocol Analysis Set (PPAS), as confirmatory analysis.

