7.8. Interim Analyses

After half of the subjects completed the 1-year follow-up timepoint, an interim analysis (secondary endpoints assessment only) will be conducted for regulatory purpose.

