7.9. Evaluation of Objectives

Primary Objective and Endpoint

The primary objective of this investigation is to confirm the efficacy of ProGrip™ Self-gripping Polyester Mesh to reduce the incidence of incisional hernia within 24 months post-operatively in subjects undergoing procedure with midline laparotomies.

The primary endpoint is the incisional hernia rate within 24 months of midline laparotomy assessed by CT-scan and physical examination including hernia clinical examination.

Statistical analysis of primary endpoint will be comparative. Binomial one-way test will be used to compare the observed ProGrip™ Self- gripping Polyester Mesh incisional hernia incidence rate to the 20% theoretical incidence rate (from no prevention population), using a two- sided alpha-level of 5%.

Primary endpoint will be measured using Performance Analysis Set; a confirmatory analysis of primary endpoint will be run using Per Protocol Analysis Set.

Secondary objective and endpoints

The secondary objective of this investigation is to confirm the safety of ProGrip™ Self-gripping Polyester Mesh through the occurrence of adverse device effects or procedure related adverse events following the use of ProGrip™ Self-gripping Polyester Mesh in subjects undergoing procedures with midline laparotomies.

To confirm the safety of ProGrip™ Self-gripping Polyester Mesh through the occurrence of adverse device effects or procedure related adverse events following the use of ProGrip™ Self-gripping Polyester Mesh in subjects undergoing procedures with midline laparotomies.

The following secondary endpoints will be assessed:

- Adverse event (AE) incidence reported by number, severity, seriousness and relationship to the procedure and device from the surgery to the 24-month visit: AE incidence will be measured on Safety Analysis Set.
- Time to incisional hernia occurrence: will be measured using Kaplan Meier estimates, and based on SAS, and PPAS.
- Post-operative pain at the site of surgery: will be measured on SAS and PPAS, at each postoperative timepoint: Day0 (after surgery), Day1, Day8, Day30, Month12 and Month24.
- Quality of life: will be measured on all, PAS, SAS, and PPAS, using Club Hernie QOL questionnaire, combining qualitative and quantitative data, at Month1, Month12 and Month24.
- Patient satisfaction: at 12 then 24 months, measured on PAS, PPAS and SAS
- Surgeon satisfaction, measured on PAS, SAS, and PPAS

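### SAP 7.10 widens the adverse device effect definition to any procedure-related event, contradicting SAP section 2 and protocol Table 4

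*SAP*

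**What the plan says.** The SAP defines an ADE twice.

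- **SAP section 2:** "Adverse event related to the use of an investigational medical device". The notes extend this to faults in instructions, deployment, implantation, operation, malfunction and use error. They do not mention the index operation. Protocol Table 4 gives the same definition with equivalent notes.
- **SAP 7.10:** "An Adverse Device Effect is an Adverse Event related to device and/or procedure". The word for procedure is not limited to mesh placement. The sentence is current text, and the SAP change history shows it as part of the version 2.0 update of 7.10.

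Two further categories are built on ADE in SAP section 2.

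- **SADE:** "Adverse device effect that has resulted in any of the consequences characteristic of a serious adverse event".
- **USADE:** "Any serious adverse device effect which by its nature, incidence, severity or outcome has not been identified in the current version" (the reference is to the risk analysis report).

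Protocol Table 4 has three separate relatedness categories: device, mesh placement procedure and index procedure. The secondary objective in SAP 7.9 also treats device effects and procedure events as two things: "through the occurrence of adverse device effects or procedure related adverse events".

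SAP 7.10 calls for listings on the Safety Analysis Set, and for MedDRA analyses by System Organ Class and Preferred Term, of AEs, SAEs, ADEs, SADEs and U(S)ADEs.

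**The concern.** The programmer has to choose one of two definitions that give different answers for the same event. A complication due solely to the standard-of-care operation is not an ADE under section 2 or Table 4, but it is one under the literal wording of 7.10.

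This matters because the study is meant to confirm the safety of the device, and ADE and SADE outputs are where a reader looks for harm attributed to it. Under 7.10 those outputs would carry laparotomy complications under a device label. SAP section 8 gives non-primary outputs only Level III validation, which is the original programmer's own visual check. No independent programming step is planned that would expose the choice.

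**Working it through.** No figure in the plan is in dispute, so the check is a comparison of text.

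**Step 1. Classify each type of event under both definitions.**

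| Event, by Table 4 category | SAP section 2 / Table 4 | SAP 7.10, literal |
|---|---|---|
| Device related | ADE | ADE |
| Mesh placement procedure related | ADE where the notes on deployment or implantation apply | ADE |
| Index procedure related only | Not an ADE | ADE |

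The clear disagreement is in the third row. The second row differs only where a mesh-placement event falls outside the notes.

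**Step 2. Compare with what is collected.** Protocol 13.1 and 16.1 restrict collection to device- and procedure-related events, and 13.5 lists the same scope for reporting. Protocol 11.10 describes the recorded AEs in nearly the words that SAP 7.10 uses for ADEs. The literal 7.10 ADE set is therefore almost the whole collected AE set. It is not quite identical, for two reasons: protocol 13.8 requires every death to be reported, related or not, and 13.5.1 has a class for events whose relationship is unknown.

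**Step 3. Follow the definition downstream.** SADE is a serious ADE, so it moves with the ADE definition. USADE is a serious ADE absent from the risk analysis report, so it moves too, subject to that extra condition.

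**Step 4. Test whether protocol 13.5.1 removes the conflict.** One sentence there treats complications of a procedure as not related if that procedure would have been carried out without the device. It can be read in two ways.

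- *Unrelated to device and procedure alike.* Index-only events would then stay out of the ADE set even under 7.10. But the same paragraph requires serious events related to the index procedure to be distinguished, and Table 4 defines that category. This reading would leave the category almost empty.
- *Not related to the device.* This fits both the paragraph and Table 4. Under it, 7.10 brings index-only events in.

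The second reading is the more coherent. Under either one, the SAP still holds two ADE definitions that differ in wording.

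**Step 5. Find what is not touched.** The secondary endpoint in SAP 7.9 is "Adverse event (AE) incidence reported by number, severity, seriousness and relationship to the procedure and device from the surgery to the 24-month visit". It does not use the ADE label, so it still reports by relationship. The primary endpoint is hernia incidence and does not depend on AE classification.

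**The case against.** The best defence is that 7.10 is a deliberate operational reading. Protocol 13.5.1 describes causality in terms of device use taken together with the medical-surgical procedure, and section 2 defines an ADE by use of the device. Putting these together gives something like the 7.10 sentence. This may explain where the sentence came from. It does not reconcile it with Table 4, which separates the index operation, or with the secondary objective, which names device effects and procedure events separately.

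The second defence is that safety is assessed elsewhere: 7.10 itself says that the secondary endpoints cover it, and 7.9 reports by relationship. That stands and limits the harm. It does not correct the 7.10 outputs.

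A reader might infer more than the documents support on four points.

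- **Device effects could not be told apart within the 7.10 outputs.** No table or listing shells are given, and a listing could show attribution beside each event.
- **The label will reach the regulatory interim analysis.** SAP 7.8 says "an interim analysis (secondary endpoints assessment only) will be conducted for regulatory purpose", but the secondary endpoints listed in 7.9 contain no ADE count, and nothing says that the 7.10 outputs are part of the interim.
- **The inflation has a known size.** SAP 7.1.3 gives the denominator ("Safety Analysis Set: includes all enrolled subjects"), and at least 135 are planned. The number of subjects with only index-related events is unknown, so any percentage would rest on an invented count.
- **A new attribution field is needed.** The list of AE data in protocol 13.5 is expressly open-ended, and the secondary endpoint already requires relationship to procedure and device.

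**Conclusion.** The contradiction is real and should be corrected before the safety outputs are programmed. Followed literally, SAP 7.10 would classify nearly all collected AEs as ADEs, including those due only to the index operation, and SADE and USADE would follow.

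The scope is narrow: the descriptive listings and System Organ Class / Preferred Term outputs of 7.10. The error runs towards overstating device effects. Its size cannot be computed from the documents. The primary analysis, the sample size and the 7.9 AE incidence are unaffected.

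The conclusion that index-only events enter the ADE set rests on reading the exclusion in protocol 13.5.1 as meaning not device-related. That is the reading that leaves Table 4's index-procedure category with a purpose. The finding that the SAP contains two conflicting definitions does not depend on it.

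**What to change.** 1. In SAP 7.10, replace the ADE sentence with the section 2 / Table 4 definition, including its notes, and add that events related only to the index procedure are not ADEs.
2. Derive the ADE, SADE and U(S)ADE outputs from that definition, using the recorded relationship to device and procedure.
3. In protocol 13.5.1, reconcile with Table 4 both the sentence on complications that are not related and the phrase that folds the medical-surgical procedure into device use.

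The cost is one SAP sentence, the derivation of the flags, and a clarification of two phrases in the protocol. ADE counts in the 7.10 outputs will be smaller than under the present wording.

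One check is needed first. Protocol 13.5.1 expressly requires the split between device, index procedure and mesh placement only for serious events. The sponsor should confirm that the relationship recorded for non-serious events also separates the index procedure from mesh placement.

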7.11. Health Outcomes Analyses

Health outcomes analyses are already part of primary and secondary endpoints analyses, as described previously.

7.12. Changes to Planned Analysis

Any major change in planned analysis as described in this SAP would result in SAP amendment.

8. Validation Requirements

Validation level I will be applied for primary endpoint analysis only.

Validation level III will be applied for any other study endpoint.

Validation levels are defined as follows:

- Level I: The peer reviewer independently programs output and then compares the output with that generated by the original Statistical Programmer.
- Level II: The peer reviewer reviews the code; where appropriate, performs manual calculations or simple programming checks to verify the output.
- Level III: Original Statistical Programmer performs a visual inspection of the code and output to confirm functionality.

9. References

4. 12. El-Khadrawy OH, Moussa G, Mansour O, Hashish MS. Prophylactic prosthetic reinforcement of midline abdominal incisions in high-risk patients. *Hernia.* 2009;13(3):267-74. doi: 10.1007/s10029-009-0484-3. PubMed PMID: 19262985.
5. 13. Garcia-Urena MA, Lopez-Monclus J, Hernando LA, Montes DM, Valle de Lersundi AR, Pavon CC, et al. Randomized controlled trial of the use of a large-pore polypropylene mesh to prevent incisional hernia in

colorectal surgery. *Ann Surg.* 2015;261(5):876-81. doi: 10.1097/SLA.0000000000001116. PubMed PMID: 25575254.

- 6. 14. Gutierrez de la Pena C, Medina Achirica C, Dominguez-Adame E, Medina Diez J. Primary closure of laparotomies with high risk of incisional hernia using prosthetic material: analysis of usefulness. *Hernia.* 2003;7(3):134-6. doi: 10.1007/s10029-003-0124-2. PubMed PMID: 12687426.
